3.5.3 Exploratory Objectives

No formal acceptance criteria.

4 Sample Size

Based on previous studies, SD for relative VAS is assumed to be 35mm. A sample size of 60 subjects per group has 90% power of passing a 10mm Non-Inferiority (NI) criteria, assuming a true average of 5mm in favor of Nucleus (2-sided 95% CI for the mean). A sample size of minimum 45 subjects per group is sufficient to provide at least 80% power (this lower sample size may be used for Group 2, Group 3 and Group 4). This sample size applies to each subgroup for which a NI (or superiority) claim is desired.

5 Intended Statistical Software

This document was generated with R version 3.3.2 (2016-10-31) and the following packages (version) were used: assertthat (0.1), base (3.3.2), BDbasics (0.1.11), colorspace (1.3.2), datasets (3.3.2), ggplot2 (2.2.0), graphics (3.3.2), grDevices (3.3.2), grid (3.3.2), gtable (0.2.0), lattice (0.20.34), lazyeval (0.2.0), magrittr (1.5), methods (3.3.2), munsell (0.4.3), nlme (3.1.128), plyr (1.8.4), Rcpp (0.12.13), reshape2 (1.4.2), rJava (0.9.8), scales (0.4.1), stats (3.3.2), stringi (1.1.2), stringr (1.1.0), tibble (1.2), tools (3.3.2), utils (3.3.2), xlsx (0.5.7), xlsxjars (0.6.1), xtable (1.8.2).

The study will be conducted within the same environment or more recent versions.

6 Data

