13.1 Sample Size Determination

Based on previous studies, SD for relative VAS is assumed to be ~35mm. A sample size of 60 subjects has 90% power of passing a 10mm NI criteria, assuming a true average of 5mm in favor of Nucleus (2-sided 95% CI for the mean). A sample size of 45 subjects is sufficient to provide 80% power. These sample size apply to each subgroup for which a NI (or superiority) claim is desired.

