7.2.2.1 Analysis of Relative VAS Score

For each outcome measured on a relative VAS, a two-sided 95% confidence intervals will be calculated for the average rating. A modeling approach will be used to adjust for the order effect (because of the often observed bias towards favoring the last PN used). A linear model will be used to evaluate the pen needle group effect on the response to test whether the groups can be combined (a p-value < 0.05 for the pen needle group effect indicates non-poolability). In the model, the order of the pen needles used and the group to which the subject belongs based on their currently used or assigned pen needle will be used as covariates. LS means with CI will be obtained from the model and tested for non-inferiority, followed by superiority.

- If the lower bound of the CI is $> -10\text{mm}$, we can conclude in non-inferiority.
- If the lower bound of the CI is $> 0\text{mm}$, we can conclude in superiority.

Additional analysis: a *wash-in* indicator and an *Asian* indicator may be used to investigate these effects, as well as a site effect.

```
> #####
> ## Example R code to fit a linear model
> #####
> ##
> ## fitting the model
> model.fit=lm(vas_analysis ~ (NUCL_ORDER + PN_GROUP + ASIA)^2 + WASH_IN,
+             data=dataset, na.action=na.omit)
> #ANOVA table
> ## if p-value for PN_GROUP < 0.05, results not poolable across Groups
> anova(model.fit)
```

Analysis of Variance Table

Response: vas_analysis

	Df	Sum Sq	Mean Sq	F value	Pr(>F)
NUCL_ORDER	1	192	191.7	0.0928	0.7612
PN_GROUP	3	2757	919.0	0.4446	0.7215
ASIA	1	3215	3215.0	1.5554	0.2144
WASH_IN	1	751	750.8	0.3632	0.5477
NUCL_ORDER:PN_GROUP	3	3991	1330.3	0.6436	0.5882
NUCL_ORDER:ASIA	1	131	130.8	0.0633	0.8017
PN_GROUP:ASIA	3	308	102.6	0.0496	0.9853
Residuals	139	287317	2067.0		

```
> ##example contrast for the different pen needle groups
> ## given results not poolable,
> ## to identify which groups are not poolable
> ##
> model.fit=lm(vas_analysis ~ NUCL_ORDER + PN_GROUP,
+             data=dataset,
+             na.action=na.omit)
> ##
> library(multcomp)
> confint(glht(model.fit, linfct = mcp(PN_GROUP = "Tukey")))
```

Simultaneous Confidence Intervals

Multiple Comparisons of Means: Tukey Contrasts

```
Fit: lm(formula = vas_analysis ~ NUCL_ORDER + PN_GROUP, data = dataset,
na.action = na.omit)
```

Quantile = 2.5914

95% family-wise confidence level

Linear Hypotheses:

	Estimate	lwr	upr
Group 2 - Group 1 == 0	-9.0440	-33.6940	15.6060

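### The stated 60 or 45 subjects per group is extended to superiority claims, but under the plan's own assumptions superiority power is only 19% or 15% per group and about 60% with all 240 subjects

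*SAP*

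**What the plan says.** The sample-size text is nearly the same in SAP section 4 and Protocol 13.1. The SAP states that "SD for relative VAS is assumed to be 35mm" and that "A sample size of 60 subjects per group has 90% power of passing a 10mm Non-Inferiority (NI) criteria, assuming a true average of 5mm" in favour of the new needle, judged on a two-sided 95% confidence interval. For the smaller size it says "A sample size of minimum 45 subjects per group is sufficient to provide at least 80% power", and it allows that size for Groups 2, 3 and 4.

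Both documents then widen the scope. The SAP says "This sample size applies to each subgroup for which a NI (or superiority) claim is desired"; the protocol says "These sample size apply to each subgroup for which a NI (or superiority) claim is desired". Neither gives a second effect size, or any power figure, for superiority.

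Superiority is a formal conclusion in the plan. SAP 3.5.1 sets its criterion at 0 mm, and SAP 3.5.2 applies the primary criteria to seven secondary VAS endpoints. The decision rule in SAP 7.2.2.1 is "If the lower bound of the CI is $> 0\text{mm}$, we can conclude in superiority", and Protocol 13.3 has the same rule. The example results table in SAP 11.2.1 (Table 4) has a superiority verdict for each group and for all groups combined.

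**The concern.** A sample size is adequate for a given test at a given assumed effect. Here the assumed effect is +5 mm. Against the non-inferiority bound of -10 mm the distance to be detected is 5 - (-10) = 15 mm; against the superiority bound of 0 mm it is 5 - 0 = 5 mm. With the SD unchanged, one sample size cannot give similar power for both tests, yet the text presents the size as applying to either claim.

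The study's stated purpose is to support marketing claims (Protocol 1.0, SAP 3.1), where superiority matters. A reader of the sample-size section would take 60 or 45 per group as enough for a group-level superiority claim. If such a test then failed, the failure could be read as evidence of no preference, when on the planning assumptions it was the likely outcome.

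**Working it through.** **Inputs.** From SAP section 4 and Protocol 13.1: SD 35 mm, true mean +5 mm, two-sided 95% CI, n = 60 or 45 per group. From the acceptance criteria and SAP 7.2.2.1: bounds of -10 mm (non-inferiority) and 0 mm (superiority). From Protocol 3.1: 240 evaluable subjects in total. If Groups 2 to 4 each use the permitted 45, the total is 60 + 3 × 45 = 195.

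**Formula.** Each subject gives one relative VAS score, signed so that positive values favour the new needle. The test is therefore one-sample:

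power = P( T′ > t(0.975, n-1) ), where T′ is noncentral t with n-1 degrees of freedom and noncentrality d·√n / 35, and d is the true mean minus the bound.

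**Step 1: reproduce the plan's figures (non-inferiority, d = 15 mm).**
- n = 60: noncentrality 15 × √60 / 35 = 3.32, critical t 2.001, power 90.4%.
- n = 45: noncentrality 15 × √45 / 35 = 2.87, critical t 2.015, power 80.3%.

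Solving for the smallest n returns exactly 60 for 90% and 45 for 80%, so the formula matches the plan's figures.

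**Step 2: change only the bound (superiority, d = 5 mm).**

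| n | Noncentrality | Superiority power |
|---|---|---|
| 45 (one group) | 0.96 | 15.3% |
| 60 (one group) | 1.11 | 19.2% |
| 195 (combined, Groups 2–4 at 45) | 1.99 | 51.0% |
| 240 (combined, all groups at 60) | 2.21 | 59.6% |

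**Step 3: what superiority would need.**
- At +5 mm: 387 subjects per claim for 80% power, 517 for 90%.
- At the stated sizes: a true mean of 14.9 mm for 90% at n = 60, and 14.9 mm for 80% at n = 45. That is about three times the planning value.

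**Step 4: sensitivity.**
- Normal approximation: 19.7% (n = 60), 15.8% (n = 45), 60.0% (n = 240).
- LS mean from the group model with pooled residual degrees of freedom: 19.5% and 15.7% per group.
- One-sided 5% test, which is not what the plan specifies: 29.1%, 24.2% and 71.3% for n = 60, 45 and 240.
- True mean +10 mm, twice the planning value: 58.6% at n = 60 and 46.6% at n = 45.
- SD 30 mm: 24.5% (n = 60) and 19.3% (n = 45). SD 40 mm: 15.7% and 12.7%.

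None of these brings per-group superiority power near 80%.

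**The case against.** The strongest reply is that the documents never state a power for superiority. The 90% figure is tied to the 10 mm criterion, and the last sentence can be read as scope only: the number is needed in each subgroup where a claim is wanted, not in total. It is also ordinary practice to size for non-inferiority and then read superiority from the same interval, and that does not commit the sponsor to 80–90% power for the second step. No stated figure is miscalculated, low power does not inflate the false-claim rate, and the primary objective is the combined analysis, where success is somewhat more likely than failure at n = 240.

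Most of this is right. Testing non-inferiority and then superiority is valid, the non-inferiority numbers are sound, and nothing here concerns type I error. How a missed superiority result would be interpreted is a risk; the documents do not say.

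The scope reading does not rescue the sentence, however. In a sample-size section, directly after the power figures, saying that a size applies to a superiority claim presents it as adequate for that claim, and no other assumption is offered. If the sponsor expects an effect well above 5 mm, the plan should say so. The large means in the SAP's example tables cannot fill that gap, because SAP section 11 says those tables come from unrepresentative test data.

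**Conclusion.** The concern holds. Under the plan's own assumptions (true mean +5 mm, SD 35 mm, two-sided 95% CI), the stated sizes give superiority power of 19.2% at 60 and 15.3% at 45 per group. A group-level superiority test is therefore about four times as likely to fail as to succeed at n = 60 (80.8 / 19.2 = 4.2) and more so at n = 45 (84.7 / 15.3 = 5.5).

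These ratios apply to single groups, which are secondary objectives. For the combined primary analysis, power is about 60% with 240 subjects and 51% with 195. It would fall further if groups are left out as non-poolable under SAP 7.2.2.

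The fault lies in what the sample-size section says about superiority. The non-inferiority sizing, the analysis and the error rate stand.

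**What to change.** In SAP section 4 and Protocol 13.1, remove the reference to superiority from the last sentence and state that 60 or 45 subjects per group gives 90% or 80% power for non-inferiority only. Then add one of the following:

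- the superiority power at the planning assumption: about 19% (n = 60) and 15% (n = 45) per group, and about 60% for 240 subjects combined; or
- the condition under which the stated power would hold for superiority: a true mean of about 15 mm.

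Say in the same place that superiority will still be tested after non-inferiority as planned, so that the edit is not read as dropping those tests.

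The cost is about two sentences in each document. Enrolment, analysis and decision rules do not change. The one drawback is that a less favourable figure becomes visible.

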6.1 Database Information

The input data will consist in several csv (comma separated values) files exported from Clinindex.

Files will be saved in

[https://svn.bdx.com:8443/svn/stats_and_dm/DM and Stats Outputs/DBC/DBC-17NUCLS07/Data](https://svn.bdx.com:8443/svn/stats_and_dm/DM_and_Stats_Outputs/DBC/DBC-17NUCLS07/Data) and read directly into R for analysis.

6.2 Analysis Population Set(s)

Two population will be defined:

- Per-Protocol (PP) Population: Excludes subjects or outcomes based on significant protocol deviations
- Intent-to-Treat (ITT) Population: Includes all randomized subjects, regardless of protocol deviations or whether they followed the randomization.

The primary analyses will be performed on the PP population and all conclusions drawn from those analyses. Analysis based on IIT population will be for information only and presented in Appendix. The number of subjects enrolled, randomized, withdrawn, who completed and who are excluded will be summarized per PP and ITT populations.

Demographic information and Diabetes history collected for all subjects randomized will be tabulated.

Data from all subjects will be included in the summary of safety parameters.

Analysis of relative VAS will only include subjects who completed both study periods.

VAS score, $Y_{analysis}^*$ (mm), will be calculated as:

$$Y_{analysis}^* = \frac{150}{20} * Y_{recorded} - 75 \quad (1)$$

The sign of the VAS responses $Y_{analysis}^*$ will then be adjusted depending on which pen needle was used in the first and in the second period, so that the positive scores (+) will reflect preference for BD Nucleus and the negative scores (-) will reflect preference for the current pen needle. Let $Y_{analysis}$ be the final relative VAS score used for the analysis. Then:

$$Y_{analysis} = \begin{cases} Y_{analysis}^*, & \text{if BD Nucleus is provided in the 2}^{nd} \text{ period} \\ -Y_{analysis}^*, & \text{if BD Nucleus is provided in the 1}^{st} \text{ period} \end{cases} \quad (2)$$

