3.4 Treatment Allocation and Methods to Reduce Bias

The order of the pen needle type (current vs. Nucleus) will be randomized for each subject. There will be no masking or blinding in this study.

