6.2 Visit 1: Screening and Enrollment

Prior to screening subjects for eligibility for the study, the PI or designee must obtain written informed consent from all potential subjects. Once consented, subjects will be assigned a subject number.

The following will be conducted by Site Staff to determine eligibility and to collect background/demographical information:

- 6.2.1 **Demographics/Diabetes History:** Subjects will be asked a number of background and demographic questions to ensure they meet the study-specific eligibility criteria. The PI or Investigator will review the medical history information self-reported by the subject; this information will be recorded in the source documents. Information collected will include, but is not limited to age, gender and diabetes history (Type 1 or Type 2, medications including dose and methods of delivery).
- 6.2.2 **Proficiency:** Subjects will be asked to perform a mock injection into an injection pad using a BD Nano pen needle. This will demonstrate their proficiency in injecting with a pen needle and pen device. If the subject is unable to demonstrated proficiency, s/he is discontinued from the study. The study staff will use a checklist to qualify the subject.
- 6.2.3 **Randomization:** After each subject has completed the proficiency test, the subject will be assigned a randomization number based on their pen needle group (Group 1-4), which will determine the order of the pen needed used in Period 1 or Period 2.

6.2.4 Visit 1

Non Wash-in Users

- Subjects will be randomized to Nucleus pen needle for the first 15-day period, then assigned commercial 32G pen needle for the second 15-day period OR assigned to commercial 32G pen needle for the first 15-day period, then the Nucleus pen needle for the second 15-day period (See randomization schedule).
- Subject will be instructed to use only the assigned pen needle during Period 1. If the subject is assigned to the Nucleus pen needle, they will be provided enough of the assigned pen needles until their scheduled return visit of 15-days. If the subject is assigned to the commercial 32G pen needle, they will use their current pen needle until the scheduled return visit of 15 days.
- Subject will be given a Diary 1 log to report events and answer questions during Period 1. Subjects will be trained on diary documentation.

Wash-in Users

- Subjects will be assigned a wash-in randomization number to determine their pen needle group (Group 1-4).

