13.2 Data Evaluability

All data collected will be analyzed, subject to review for possible exclusion based on significant protocol deviations (e.g. failure to follow randomization scheme).

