11.3 Additional Analysis

Analysis for the primary and secondary objectives will be performed on the intent-to-treat (ITT) population for information and presented in Appendix.

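### Superiority is concluded from the per-protocol set alone, although exclusions in this unmasked preference study may be related to preference and the intent-to-treat result cannot alter a claim

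*SAP*

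**What the plan says.** SAP 6.2 defines two analysis sets.

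- **PP:** "Excludes subjects or outcomes based on significant protocol deviations".
- **ITT:** "Includes all randomized subjects, regardless of protocol deviations or whether they followed the randomization".

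Only PP decides: "The primary analyses will be performed on the PP population and all conclusions drawn from those analyses". For the other set, the same section says "Analysis based on IIT population will be for information only and presented in Appendix" (IIT is evidently a misprint for ITT). SAP 11.3 repeats this: "Analysis for the primary and secondary objectives will be performed on the intent-to-treat (ITT) population for information and presented in Appendix".

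SAP 3.5.1 and 7.2.2.1 test non-inferiority (lower confidence limit above -10 mm) and then superiority (lower limit above 0 mm) from the same interval. No separate set is named for superiority.

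Neither document says what makes a deviation significant. Protocol 13.2 gives one example: all data are analysed, "subject to review for possible exclusion based on significant protocol deviations (e.g. failure to follow randomization scheme"). Protocol 3.4 states: "There will be no masking or blinding in this study".

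SAP 6.2 also limits the relative VAS analysis to subjects who completed both periods. That rule is not confined to PP, so it applies to ITT as well.

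**The concern.** The primary outcome is which needle the subject preferred. Subjects are told to use only the assigned needle in each period (Protocol 6.2.4, 6.3 and 6.4). A subject who dislikes Nucleus and goes back to the familiar needle would depart from that instruction, and the departure would itself express a preference. If such subjects are removed, the mean of those who remain moves towards Nucleus.

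PP is a usual set for non-inferiority, where deviations tend to dilute a difference and make the products look alike. That reasoning does not carry over to superiority, nor to deviations that arise from the outcome itself.

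Superiority is a formal conclusion, and Protocol 1.0 says the outcomes are meant for marketing claims. If PP shows superiority and ITT does not, the plan still concludes superiority, because it has no rule for disagreement. No step requires exclusions to be settled before the VAS scores are seen.

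**Working it through.** **Inputs from the documents.** SD 35 mm; assumed true mean +5 mm; 60 or 45 subjects per group; two-sided 95% CI (SAP 4). Non-inferiority limit -10 mm and superiority limit 0 mm (SAP 3.5.1). Target 260 subjects, of whom 20 are an allowance for loss to follow-up or other significant deviations (Protocol 3.1).

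**The plan's own figure.** The distance from +5 to -10 mm is 15 mm. The noncentrality is 15/(35/√n), which is 3.32 at n = 60 and 2.87 at n = 45. The noncentral t distribution gives power of 90.4% and 80.3%. The stated 90% and 80% reproduce and are not in dispute.

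**Assumptions for the scenarios** (not in the documents). N = 260 randomized with a true all-randomized mean of 0 mm. Of these, k completers are excluded from PP and have average score e, with e = -25 or -50 mm. All 260 answered the comparative question.

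**Formulas.**
- PP mean = -k·e/(N - k)
- Standard error = 35/√(N - k)
- False-superiority rate = P(T > t(0.975, N - k - 1)), with T noncentral t and noncentrality PP mean / standard error

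Example with k = 20 and e = -50: PP mean = 1000/240 = 4.17 mm; standard error = 35/√240 = 2.26 mm; noncentrality = 1.84; rate = 45%.

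| Excluded k | PP mean, e = -25 / -50 (mm) | False superiority, e = -25 / -50 |
|---|---|---|
| 0 | 0 | 2.5% |
| 3 | +0.3 / +0.6 | 3.4% / 4.5% |
| 5 | +0.5 / +1.0 | 4.1% / 6.5% |
| 10 | +1.0 / +2.0 | 7% / 14% |
| 20 | +2.1 / +4.2 | 15% / 45% |

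**One group.** With 5 of 65 excluded (one quarter of 20 and of 260), the PP means are +2.1 and +4.2 mm and the rates 7% and 15%.

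**Non-inferiority.** If the all-randomized mean is -10 mm and the excluded subjects score 25 or 50 mm below that, the same shifts and rates apply to a false non-inferiority conclusion.

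**Scale.** The plan's assumed benefit is +5 mm. A PP mean of +5 mm in 240 subjects, with 20 excluded at -50 mm, is an all-randomized mean of (240 × 5 - 20 × 50)/260 = +0.8 mm.

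**The case against.** A reader might infer that exclusions will favour Nucleus, that reverting to the old needle is the most likely deviation, and that 15% to 45% is the expected error. The documents support none of these.

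- **Mechanism.** Reversion is never named as a significant deviation. It is an inference from the instruction to use only the assigned needle and from the example in Protocol 13.2. That example could equally mean needles dispensed in the wrong order, which has nothing to do with preference. Protocol 6.2.4 says of non-wash-in subjects assigned to the commercial needle that "they will use their current pen needle until the scheduled return visit of 15 days". This suggests that they have those needles at home, but says nothing about what they do in the Nucleus period. Visit-window departures or use of prescription analgesics are other candidates, and some exclusions could run against Nucleus.
- **Size.** The allowance of 20 includes subjects lost to follow-up. They do not reach the Visit 3 questionnaire, and the completer rule drops them from the VAS analysis in both sets, so they cannot create a gap between PP and ITT. Only completers removed for deviations count, and no number is given for them. With 3 to 5 such exclusions the error is 3.4% to 6.5%.
- **Existing safeguards.** PP is a usual set for non-inferiority, which is the criterion on which the study is powered. ITT results are reported, exclusions are listed with reasons (SAP 11.1.2), and disposition is given for both sets.

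All of this limits the size of the problem and how certain it is. It does not answer the narrower point. The safeguards would make a disagreement visible, but they cannot change the conclusion, and nothing fixes the exclusions in advance.

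**Conclusion.** The concern holds as a weakness in how conclusions are drawn; it is not a demonstrated bias. All claims, including superiority, depend on a set whose exclusion rule is undefined, in an unmasked study where exclusion may be related to the primary outcome.

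The direction and size are unknown. If every exclusion is a completer who preferred the current needle by 25 to 50 mm on average, the nominal 2.5% error rises modestly with 3 to 5 exclusions and materially with 10 or more. The row for 20 is a worst case. All rows assume SD 35 mm and complete ITT scores, and exclusions unrelated to preference leave the error at 2.5%. The objection is strongest for superiority. For non-inferiority, PP is a reasonable set but should not decide alone.

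**What to change.** Amend SAP 6.2 and 11.3 as follows.

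1. Conclude superiority from the ITT set, meaning all randomized subjects with a comparative questionnaire. Keep the sign coding of equation (2), by the needle provided in each period. Coding by the needle used would be ambiguous for anyone who used both in one period.
2. Conclude non-inferiority on the VAS outcomes only if the lower limit exceeds -10 mm in both PP and ITT.
3. Define significant deviations, and sign off the list of excluded subjects and outcomes before VAS scores are joined to needle order.
4. Add a sensitivity analysis for randomized subjects without a VAS score. The completer rule removes them from ITT too, so moving to ITT does not by itself cover subjects who left before Visit 3.

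The cost is mainly SAP wording, since both analyses are already planned. The new work is a deviation list, a sign-off step and one sensitivity analysis. The downside is that some claims become slightly harder to make.
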